Exploratory Specific Aim 1. We will use qualitative methods to explore participants' perceptions of the exercise interventions in the high and low-intensity exercise groups, respectively, at 52-week follow-up.

Exploratory Specific Aim 2. In an exploratory specific aim, in up to 15 people with PAD and a body mass index $> 28 \text{ kg/M}^2$ who previously participated in the LITE Study or who were evaluated for participation, we will test the feasibility and efficacy of a 16-week weight loss intervention combined with the LITE home-based exercise intervention. The primary goals will be to determine whether it is feasible and effective to add a weight loss intervention to the LITE home-exercise intervention in people with PAD who are overweight. We will determine whether this modification of the LITE intervention (weight loss combined with the LITE home-based exercise intervention) can improve six-minute walk distance in people with PAD.

Exploratory Specific Aim 3. In an exploratory specific aim, in up to 30 people with PAD, we will determine whether, compared to placebo, nitrate-rich beetroot juice acutely improves six-minute walk distance or the short physical performance battery (SPPB), two-hours after nitrate-rich beetroot juice or placebo ingestion. We will also collect preliminary data to determine whether, as compared to placebo and as compared to nitrate-rich beetroot juice, far-red light (approximately 660 nm) alone and the combination of far-red light + nitrate-rich beetroot juice acutely increase plasma nitrite and improve six-minute walk distance, four meter walking velocity at usual or fast pace, or the SPPB, approximately two to three hours after far-red light treatment alone and the combination of far-red light treatment with nitrate-rich beetroot juice.

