AA. In follow-up to the above, and for exploratory aim #3, we will assess the acute effects of nitrate-rich beetroot juice, compared to placebo, on change in six-minute walk distance, four-meter walking velocity at usual pace, four-meter walking velocity at fast pace, and the SPPB. Participants who sign written informed consent will be assigned to either nitrate-rich beetroot juice, described above, a matching placebo that is made by the same company that does not include the nitrate-rich beetroot juice, or 10 minutes of light therapy with a 660 nm light. They will be asked to perform a six-minute walk, four meter walking velocity at usual and fastest pace, and the SPPB without consuming any beverage at the first visit for this substudy. Approximately 1-5 weeks later, they will return for repeat measures. However, prior to the repeat measures, performed approximately 1-5 weeks after the initial measure, they will either consume one drink of nitrate-rich beetroot juice, consume the matching placebo, or receive light therapy. Blood will be obtained prior to the intervention (drink or light therapy) and at approximately 2.5 hours after ingesting the drink or 10 minutes after the light therapy. The blood will be obtained for measurement of nitrate and nitrite and potentially other blood measures for research. Participants assigned to light therapy will receive up to 10 minutes of light therapy with a 660 nm light (<https://mitoredlight.com/products/mitomid>) prior to the second blood draw at the second visit. The six-minute walk, the four-meter walk at usual and fastest pace, and the SPPB will be performed immediately after the blood draw. Participants may be asked to return for a third visit, in which they receive both nitrate-rich beetroot juice and the light therapy. At this third visit, participants will undergo a blood draw. They will then receive the nitrate-rich beetroot juice. Approximately 2.5 hours later, they will receive the 10 minutes of light therapy. Immediately after the light therapy they will have plasma measured for nitrite and they will undergo

PROTOCOL TITLE: Low InTensity Exercise intervention in PAD: The LITE Trial

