functional performance measures (six-minute walk, four meter walks, and SPPB) immediately after the blood draw. In statistical analyses, the degree of change in each outcome (six-minute walk distance, four-meter walking velocity at usual pace, four-meter walking velocity at fastest pace, or the SPPB) between the initial measure and the measure obtained approximately 1-5 weeks later after consumption of the study drink and/or the light therapy, will be assessed and compared with those who received placebo. We will also analyze the association between the combination of the therapies (nitrate-rich beetroot juice + light therapy) and the individual therapies for the outcomes of increases in plasma nitrite and the degree of improvement in the functional measurements.

Specimens may be shipped to Wake Forest University for measurement of nitrates and nitrites, for participants who agreed to the optional beetroot juice portion of the study.

Procedures performed to lessen the probability or magnitude of risks.

A. Adequacy of protection against risks and methods to minimize potential risks. *Overview of protection against risks.* Prior to beginning data collection, all study coordinators undergo training and are certified by [name] using a detailed checklist for each data collection element (see Appendix C). Research coordinators are certified in each element of the study visit including obtaining informed consent, administering questionnaires, protecting confidentiality of collected data, performing the six-minute walk, and performing the ankle brachial index. [name] re-certifies coordinators every six months to ensure continued adherence to protocol. Those not adhering to all aspects of the protocol undergo additional training followed by re-certification.

All research staff members have completed human subjects training required by Northwestern's institutional review board (IRB). This training includes education about the importance of maintaining confidentiality of personal health information. The study principal investigator or a co-investigator is available to answer questions that arise during the informed consent process as needed.

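### Exploratory Aim 3: the beetroot-plus-light combination is given only at an optional third visit, so its walking and SPPB comparisons cannot be separated from visit order or from who returns (minor)

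*Combined protocol and SAP*

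**What the plan says.** Section 1.2, Exploratory Specific Aim 3, has a lead question and an additional one. The lead question is "in up to 30 people with PAD, we will determine whether, compared to placebo, nitrate-rich beetroot juice acutely improves six-minute walk distance". The additional one begins "We will also collect preliminary data to determine whether, as compared to placebo and as compared to nitrate-rich beetroot juice" and goes on to ask whether "far-red light (approximately 660 nm) alone and the combination of far-red light + nitrate-rich beetroot juice acutely increase plasma nitrite" and improve walking measures or the SPPB.

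Section 9.2, item AA, gives the schedule:

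- **Visit 1:** functional tests with no study drink.
- **Visit 2, about 1 to 5 weeks later:** "they will either consume one drink of nitrate-rich beetroot juice, consume the matching placebo, or receive light therapy". Blood is drawn before and after treatment, and the functional tests follow.
- **Visit 3, by invitation:** "Participants may be asked to return for a third visit, in which they receive both nitrate-rich beetroot juice and the light therapy". Blood is drawn before the juice and again after the light, and the functional tests follow.

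Item AA gives no rule for who is invited to visit 3, no interval between visits 2 and 3, and no third visit with placebo or a single therapy. For analysis, it compares change from the first visit with change in placebo recipients, and adds: "We will also analyze the association between the combination of the therapies (nitrate-rich beetroot juice + light therapy) and the individual therapies", for plasma nitrite and the functional measures. It names no model and no adjustment for visit or for repeated measures on the same person.

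**The concern.** Placebo and the single therapies are observed only at visit 2. The combination is observed only at visit 3, in those invited and willing to return, and always after a visit-2 condition (which may have been placebo). A difference between the combination and any comparator is therefore also a difference between a third and a second visit. If those returning differ from those who do not, it is a difference between people as well.

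At stake is how the preliminary data are read. A third-visit gain with no treatment effect behind it could be reported as a benefit of combining the therapies, or a third-visit decline could hide a real one.

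**Working it through.** The plan gives no power, effect size or significance level for this aim, so there is no figure to reproduce. The check is whether the planned comparison can be estimated at all.

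**Terms, for one functional outcome measured once per visit**

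- three group levels (beetroot, placebo, light);
- visit effects v2 and v3, relative to visit 1;
- treatment effects b (beetroot), l (light) and c (combination), with placebo as reference.

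That is 3 + 2 + 3 = 8 terms.

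**Expected change from visit 1 under item AA**

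| Condition | Visit | Expected change |
|---|---|---|
| Placebo | 2 | v2 |
| Beetroot juice | 2 | v2 + b |
| Light | 2 | v2 + l |
| Combination | 3 | v3 + c + s |

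Here s is the amount by which the change in those who return differs from the change in everyone.

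**The planned contrasts**

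- Combination minus placebo: (v3 + c + s) − v2 = c + (v3 − v2) + s.
- Combination minus beetroot juice: (v3 + c + s) − (v2 + b) = (c − b) + (v3 − v2) + s.
- Combination minus light: (c − l) + (v3 − v2) + s.

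Restricting to returners and comparing each with their own visit 2 removes s, unless people were invited because of their visit-2 result. It leaves (v3 − v2) in place.

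**Rank check.** With three groups by three visits and the 8 terms above, the design matrix has rank 7. The column for the combination is identical to the column for visit 3. The model becomes estimable (7 columns, rank 7) only if the visit-3 term is deleted, which assumes v3 = 0.

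**Size.** The bias equals (v3 − v2) + s. The documents give no value for either. As an illustration with s = 0 and no true combination effect, assumed shifts of 0, 5, 10 or 20 m in six-minute walk would appear as combination effects of 0, 5, 10 or 20 m.

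**Remedies checked the same way**

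- If half of each group receives the combination at visit 2 and half at visit 3, the matrix has 8 columns and rank 8. With a separate level for each of the six group-by-order sequences it has 11 columns and rank 11. The combination effect is then estimable, assuming no carry-over.
- Adding a placebo or sham third visit also gives rank 8 of 8.

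**Plasma nitrite.** Item AA has a blood draw before dosing at visit 2 and again at visit 3. The increase can be taken from the same-day sample, so drift in level between visits largely cancels. The term s does not.

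**The case against.** The best reply is that this is an optional part of an exploratory substudy, described as preliminary, with no formal test or significance level, and that no primary or secondary aim uses it. That stands, and it sets the severity. It does not make the combination contrast interpretable.

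A reader might also infer more than the documents support:

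- **That every combination comparison is equally confounded.** Nitrite has its own pre-dose sample at visit 3, and repeat-testing practice does not apply to a blood assay.
- **That practice effects are established.** Section 9.2, item J, says the six-minute walk lacks the treadmill's learning effect. Nothing in the documents reports one for the SPPB or four-meter walks. The overlap does not depend on practice: elapsed time, expectation and selection also sit in (v3 − v2) + s.
- **That carry-over from visit 2 is present.** It is not shown; the interval is simply not stated.
- **That the first assignment is non-random.** Item AA says "Participants who sign written informed consent will be assigned to either nitrate-rich beetroot juice" or another condition and gives no method. That is silence, and it is not the cause of the overlap.
- **That the small sample proves the point.** If 30 people split equally, which the plan does not say, 10 per group would detect (1.96 + 0.84) × √(2/10) = 1.25 SD at 80% power. That measures imprecision in an independent-groups comparison. More participants on this schedule would leave the overlap untouched.
- **That the whole aim fails.** Its lead comparison, beetroot juice against placebo, is made at the same visit and does not share the problem.

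**Conclusion.** The point holds in a limited form and is minor. For the six-minute walk, four-meter walks and SPPB, the comparisons of the combination with placebo and with the single therapies overlap completely with visit order, and the between-group versions also with selection of returners. No analysis of data collected on this schedule can separate them without assuming that visit 3 would have matched visit 2 in the absence of treatment. For plasma nitrite, selection is the main remaining difference of this kind.

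The structural result needs no assumed figure. The size of any bias is unknown and cannot be estimated from the planned data. The visit-2 beetroot-versus-placebo comparison and the main trial are not affected.

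**What to change.** Choose one of two routes.

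1. **Make the comparison estimable.** Invite every substudy participant to both treatment visits, and randomize which of the two carries the combination and which carries the assigned single condition. State the interval between the visits, and analyze with visit and participant terms. The cost is up to 30 third visits in place of an optional number, and a small new randomization list: the main trial's list (section 3.1, item C) serves its own three arms and is stratified by biopsy eligibility and consent, so it cannot be used unchanged. Some single-condition measurements would also move to visit 3, so the beetroot-versus-placebo comparison would need the visit term and an assumption of no carry-over.

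2. **Keep the schedule and narrow the claim.** Remove the between-group combination comparisons from section 1.2 (Exploratory Specific Aim 3) and from the analysis text of item AA. Report visit 3 as within-person description only, with the number invited, the number attending and the reason for invitation. The cost is wording and a weaker claim.

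The second route is adequate if the substudy is meant only to inform a later design.

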- J. **Six-minute walk test.** The primary outcome is change in six-minute walk distance between baseline and 52-week follow-up. We have selected the six-minute walk as our primary outcome for several reasons. First, the six-minute walk is a well validated measure of walking endurance that better represents walking during daily life than treadmill walking performance in older people (15,71-76). Second, our prior work demonstrates that poorer six-minute walk performance is associated with higher rates of mortality and mobility loss in people with PAD (15,71). Third, treadmill walking performance is associated with a significant learning effect (77-80). However, the six-minute walk does not have this limitation (72,80). In the six-minute walk, participants walk back and forth along a 100-ft hallway for six minutes after standardized instructions to complete as many laps as possible (15,52,55,71,72). Distance covered in six minutes is recorded. The intra-class correlation coefficient for the test-retest reliability of the six-minute walk test among 156 PAD participants in our laboratory was 0.90 (p<0.001) when two six-minute walks were completed one week apart (55,72).
- K. **Four-Meter Walk.** Participants are timed walking a four-meter distance in a corridor at their usual and fastest pace. Each walk is performed twice, and the fastest walk in each pair is used in analyses.
- L. **Short Physical Performance Battery (SPPB).** *Repeated chair rises:* Participants sit in a straight-backed chair with arms folded across their chest and are timed standing from the seated position five times consecutively as quickly as possible. Timing begins with the word, “go”, and ends when the participant stands upright for the fifth time. *Standing balance:* This measure is also a component of the summary performance score. Participants are asked to hold three increasingly difficult standing positions for ten seconds each: standing with both feet together side-by-side and parallel (side-by-side stand), standing feet parallel with the toes of one foot adjacent to and touching the heel of the opposite foot (semi-tandem stand), and standing with one foot directly in front of the other (tandem stand).

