C. Six-minute walk test. The six-minute walk test may be associated with the risk of falling or coronary ischemia or dyspnea due to heart failure or lung disease. Rarely, falling during the six-minute walk test may result in a fracture. However, the research assistant who will collect these data has been trained to prevent falling. The risk of a fracture secondary to a fall during the six-minute walk test is less than 1 in 5,000.

D. Risks associated with ABI measurement. The ankle brachial index measurement consists of measuring systolic blood pressure in each extremity using a hand-held Doppler. The ABI is non-invasive, safe and does not have any known lasting side effects. During the ankle brachial index test, participants may experience discomfort from the inflated blood pressure cuff. However, this discomfort resolves immediately when the cuff is released.

PROTOCOL TITLE: Low InTensity Exercise intervention in PAD: The LITE Trial

E. **Risks associated with drawing blood:** The potential risks of drawing blood include a bruise at the site of vein puncture, inflammation of the vein, and infection. Care will be taken to avoid these complications.

F. **Risks associated with questionnaire administration and qualitative interviewing.** Participation includes a risk of loss of confidentiality regarding personal health information. However, all research staff have undergone formal human subjects training. They are trained to protect the privacy of research subject participants. *Each qualitative interview will be digitally recorded to reduce the need for note taking and to facilitate analysis. When participants consent to the study, we will use a staged consent to ask permission to record the qualitative portion of the interviews to better capture qualitative data. If a participant does not give permission for audio-recording, s/he can still participate in the study. In those cases, the designated interviewer will enter as much of the participant's responses as possible.*

G. **Risks associated with exposing the legs to far-red light for approximately 10 minutes.** There are no known risks associated with the light exposure. The light is bright and can be uncomfortable if the participant looks directly into the light. The light will be directed away from the eyes and the participant will be provided with goggles to wear during the light treatment

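### Exploratory Aim 3 compares far-red light with a placebo drink, so a light effect on the walking tests cannot be separated from differences in expectation or schedule between the arms

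*Combined protocol and SAP*

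**What the plan says.** Section 1.2, Exploratory Specific Aim 3, sets out to collect preliminary data on nitrite, walking and SPPB "as compared to placebo and as compared to nitrate-rich beetroot juice, far-red light (approximately 660 nm) alone and the combination of far-red light" plus juice. Light versus placebo is therefore a stated comparison.

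Section 9.2, item AA, gives the procedure. The alternatives to the juice are "a matching placebo that is made by the same company that does not include the nitrate-rich beetroot juice, or 10 minutes of light therapy". Before the repeat tests, "they will either consume one drink of nitrate-rich beetroot juice, consume the matching placebo, or receive light therapy". At that visit nobody receives both a drink and the light. Blood is drawn about 2.5 hours after a drink or 10 minutes after light, and "The six-minute walk, the four-meter walk at usual and fastest pace, and the SPPB will be performed immediately after the blood draw". Some participants may return for a third visit at which they take the juice and, about 2.5 hours later, have the light.

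The analysis sentence in the same item says that changes "after consumption of the study drink and/or the light therapy, will be assessed and compared with those who received placebo". Section 14.1, item G, describes the light as bright and says that "the participant will be provided with goggles to wear during the light treatment". Section 11.1 gives no test or significance level for this aim.

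**The concern.** A placebo control works when the two arms differ only in the active ingredient. The matching drink does that for the juice. It does not do it for the light: one arm sits with goggles in front of a bright device and takes no drink, while the other takes a drink and sees no device. The arms also wait for very different times before they are tested.

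The six-minute walk depends on effort, because "participants walk back and forth along a 100-ft hallway for six minutes after standardized instructions to complete as many laps as possible". Fast-pace walking and timed chair rises share this property; usual-pace walking does so less. If participants expect more, or less, from a device than from a drink, or if the length of the wait affects performance, the difference would be read as an effect of light. The combination visit has the same problem. It has no sham or placebo counterpart, and it comes later in the test sequence. What is at stake is what the light and combination walking results can be taken to show.

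**Working it through.** **Is a matched control described anywhere?** I compared the descriptions of the light, the placebo and blinding.

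| Feature | Juice | Placebo drink | Light alone | Juice + light (third visit) |
|---|---|---|---|---|
| Takes a drink | yes | yes | no | yes |
| Sits with the device and goggles | no | no | yes | yes |
| Drink to blood draw and tests | about 2.5 h | about 2.5 h | not applicable | about 2.5 h plus the light session |
| Light to blood draw and tests (9.2, AA) | not applicable | not applicable | about 10 min | immediately after |
| Visit | second | second | second | third |

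Juice and placebo drink agree on every row. Light alone differs from placebo drink on every row except the visit. The combination differs on the device and on the visit. The documents describe no sham light, no double-dummy, and no masking of participants or assessors in this substudy. The only blinding mentioned is of an independent rater of coaching calls in the main trial (section 9.2, item F).

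**Timing after light.** Section 1.2 places the light outcomes about two to three hours after light treatment, alone or combined with juice. Section 9.2, item AA, places blood and tests about 10 minutes after light alone, and immediately after light at the third visit. The two sections do not agree.

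**How much could an unmatched difference matter?** The plan states no power, split or test for this aim, so there is no figure to reproduce. The following is illustration only.

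Inputs:
- n = 10 per arm. Section 1.2 says up to 30 people; an equal three-way split is assumed.
- SD of change = 60 m (section 11.2, from the group's earlier exercise trials, not from an acute retest), or 45 m (assumed, for a shorter interval).
- Two-sided t-test at 0.05 (assumed); 18 degrees of freedom, critical value 2.101.
- True light effect = 0.
- Unmatched gain b = 5, 10, 20 or 30 m (assumed). Section 11.2 gives 30 m as a small meaningful change. It serves here only as the top of the range and is not an estimate of placebo response.

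Formulas: SE = SD × √(2/n), and noncentrality = b / SE. The rejection rate is the probability that a noncentral t falls beyond ±2.101.

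- SD 60 m: SE = 60 × √0.2 = 26.8 m.
- SD 45 m: SE = 45 × √0.2 = 20.1 m.

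| b (m) | Noncentrality, SD 60 | Rejection rate, SD 60 | Noncentrality, SD 45 | Rejection rate, SD 45 |
|---|---|---|---|---|
| 0 | 0 | 0.050 | 0 | 0.050 |
| 5 | 0.19 | 0.054 | 0.25 | 0.056 |
| 10 | 0.37 | 0.064 | 0.50 | 0.076 |
| 20 | 0.75 | 0.109 | 0.99 | 0.156 |
| 30 | 1.12 | 0.185 | 1.49 | 0.292 |

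The test is symmetric, so a difference of the same size against light gives the same rates in the opposite direction. A larger sample would not remove the bias; it would only make a biased difference more likely to reach significance.

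**The case against.** The strongest reply is that the placebo group is not untreated. Those participants swallow something that may help them and may improve for that reason. A reader might infer that the whole non-specific response falls on the light arm, so that the bias equals the full placebo gain. The documents do not support that. Only the difference in expectation between a device and a drink is unmatched, and it could be small, zero or negative. This limits the size of the problem; it does not make the comparison interpretable.

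The illustrated rates also rest on assumptions. At an unmatched gain of 5 m, the rate hardly moves from 5%. The table shows what would follow from a bias, not that one exists. This stands.

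The aim is exploratory, and the plan itself calls the light part preliminary. It never describes the light comparison as blinded or placebo-controlled. The walking instructions are standardized, so extra encouragement by staff should not be presumed. These points lower the severity. They do not remove the stated intention to compare light with placebo on walking.

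Finally, a sham made by switching off a bright light may well be recognized as inactive. That is a fair limit on the design remedy, but it does not affect the reporting remedy.

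**Conclusion.** The point holds and is minor. For light alone, any difference from placebo on six-minute walk, four-meter walks or SPPB mixes a possible light effect with unmatched expectation and a different wait before testing. For the combination, it mixes in the unmatched device and the later visit. The size and direction are unknown. Under the stated assumptions, the chance of a significant difference with no true light effect would be 5% to 19% at an SD of 60 m and 6% to 29% at 45 m.

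A reader might conclude that Exploratory Aim 3 as a whole is uncontrolled. It is not: juice versus placebo drink has a matched comparator on a matched schedule. Plasma nitrite is a laboratory measure and much less exposed to expectation, although its sampling time also differs between light and drink. The primary and secondary aims are untouched.

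**What to change.** 1. **Analysis text (section 9.2, item AA).** State that light and combination results on the walking tests and SPPB lack a matched control, are described only, and support no claim of benefit over placebo. Base any light-versus-placebo inference on plasma nitrite, and note the different sampling times. This costs a few sentences and applies even if testing is complete.

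2. **If participants are still to be tested.** Put all arms on one common schedule with a double-dummy: the placebo drink for the light group, and the inactive device with goggles for the drink groups. The drink and device already exist. If the drink interval stays as written, light participants wait about 2.5 hours longer and drink participants give about 10 more minutes. Masking of a bright light will be imperfect, so the report should say so.

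3. **Timing.** Reconcile section 1.2 with section 9.2, item AA, on when outcomes are measured after light.
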